## 1. Abstract

Sponsor Identification	Instituto de Investigación Sanitaria Puerta de Hierro [name]
Study Title	Project to enhance Dermatology E-Consultations in Primary Care Centres using Artificial Intelligence Tools.
Protocol code	LEGIT.HEALTH_DAO_Derivación_PH_2022
Protocol version and date	Version: 1.0. Date: 29/06/2022
Research Coordinator	[name] [name] Dermatology Service Puerta de Hierro Majadahonda University Hospital [name]
Principal Investigator	[name] [name] Dermatology Service Puerta de Hierro Majadahonda University Hospital [name]
Collaborating investigators	[name] Majadahonda Health Center [name] Pozuelo Health Center [name] Dermatology Service

	Puerta de Hierro Majadahonda University Hospital
Investigational centers	Puerta de Hierro Majadahonda University Hospital Majadahonda Health Center Pozuelo Health Center
Ethics Committee	Research Ethics Committee of the Puerta de Hierro Majadahonda University Hospital
Primary Objective	The main objective of this study is to validate the clinical utility of the Legit.Health platform developed by AI LABS GROUP SL in the management of patients with skin pathology by primary care physicians and dermatologists of the Puerta de Hierro Majadahonda University Hospital involved in the project.
Design	Prospective observational analytical study of a series of clinical cases with a longitudinal character.
Disease under study	Patients suspected of having the following pathologies in Primary Care: tumor pathology, inflammatory pathology, and infectious pathology
Study Population and Total Number of Subjects	100 adult patients attending their primary care center with tumor pathology, inflammatory pathology, or infectious pathology.
Calendar. Planned Duration of the Study	The study will last 5 months, with 4 months of recruitment time and 1 month for data analysis.
Ethical Considerations	The development of the study will comply with international Good Clinical Practice (GCP) guidelines, the Declaration of Helsinki in its latest active amendment, and applicable international

	and national rules and regulations. The study will not begin until approval has been obtained from the Ethics Research Committee of the Hospital Universitario Puerta de Hierro Majadahonda.
--	--

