**Variables**

The main variable aims to determine the clinical utility of the platform developed by AI LABS GROUP SL in the management of patients with skin pathology by primary care physicians and dermatologists of the Puerta de Hierro Majadahonda University Hospital involved in the project.

For this purpose, clinicians will complete the **Clinical Utility and Satisfaction Questionnaire (Annex I)**.

In addition, the following secondary variables will be collected::

- Patient demographics:
  - Sex
  - Age
- Teleconsultation data:
  - Response time
  - Response label (follow-up in primary care, shared follow-up, dermatology follow-up, insufficient or inadequate information)
- Data from the in-person consultation:

- Duration of an in-person dermatology appointment to respond to an online primary care consultation.
- Waiting time until being seen in a specialized dermatology clinic.
- Diagnosis
  - Diagnostic correlation between primary care and dermatology.
  - Number of patients referred by pathology.
  - Diagnostic correlation between primary care, dermatology, and dermatopathology (if applicable).
  - Time elapsed between the day of the primary care visit and the day of the histopathological diagnosis (if applicable).
- Primary care physician satisfaction using the Clinical Utility and Satisfaction Questionnaire (Appendix I).
- Dermatologists satisfaction using the Clinical Utility and Satisfaction Questionnaire (Appendix I).

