### **Expected sample size**

This study will recruit 100 patients. This study is designed as a proof-of-concept pilot study in which the sample size has been estimated based on the number of primary care physicians who treat patients diagnosed with skin diseases who can be seen in the primary care services of the following centers:

1. Majadahonda Health Center
2. Pozuelo Health Center

During the study recruitment period, all patients diagnosed with skin diseases who meet the selection criteria will be included.

To ensure that all primary care physicians participating in the study have sufficiently interacted with the tool, a minimum of 50 patients per primary care center is required.

The data collected from these patients during the study period will be analyzed, and based on the results, an assessment will be made as to whether it is necessary to expand the sample size to include more patients.

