## **Procedures to be performed by the specialist physician**

### **1. Consultation**

The Principal Investigator will see patients while maintaining their standard clinical routine. In the Data Collection Document (DCD), they will note the appropriateness of the patient referral. If they deem the referral to dermatology inappropriate, this will also be recorded. The initial diagnosis provided by the primary care physician, as well as their own diagnosis, will be documented. If relevant, the pathology diagnosis will also be included.

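### The calendar leaves no follow-up after the last recruit, so the secondary variables that mature after enrolment will be incomplete for late recruits, and summaries of completed intervals alone would be biased short

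*Combined protocol and SAP*

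**What the plan says.** The Abstract gives the calendar as "The study will last 5 months, with 4 months of recruitment time and 1 month for data analysis". Nothing is left between the last recruit and the analysis. No section gives a follow-up window, a data-cut date or a rule for patients whose interval is still open at closure. The section on expected sample size states "This study will recruit 100 patients" and adds that "The data collected from these patients during the study period will be analyzed".

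The Variables section (4. Methods) lists secondary variables that complete only after the enrolment visit:
- "Waiting time until being seen in a specialized dermatology clinic";
- the interval from primary care visit to histological diagnosis, where there is one;
- diagnostic correlation of primary care with dermatology, and with dermatopathology where applicable.

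In the specialist's procedures (5. Work plan, Consultation), "The Principal Investigator will see patients while maintaining their standard clinical routine". At that consultation the appropriateness of the referral is noted, and "The initial diagnosis provided by the primary care physician, as well as their own diagnosis, will be documented", with pathology added where relevant. The date of this consultation is set by routine care, with no study window.

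The main variable is the clinician questionnaire at 2 and 4 months. Separately, the Patient identification section says that patients' data will not be analysed. That conflicts with the Variables section and with the specialist's data collection.

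**The concern.** A wait, a histology result or a dermatologist's diagnosis enters the data only if it arrives before closure. Early recruits can show intervals of up to 4 months (5 if the analysis month also collects data). Late recruits can show only short ones.

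Two things are at stake. First, if waits still open at closure are left out, the completed ones are a selection of short waits, and their mean or median understates the true value. Second, diagnostic agreement and referral appropriateness would rest mainly on patients recruited early or seen quickly. Referral appropriateness carries weight because the Hypothesis section is about it and the first secondary objective concerns referral. Histology is more exposed than the clinic visit, because it usually needs further steps after it.

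**Working it through.** **The plan's own figures.** 4 + 1 = 5 months, which matches the stated duration and leaves 0 months of follow-up. There is no power calculation to reproduce.

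**Observation time.** Taking 30 days per month, recruitment runs from day 0 to day 120 and analysis ends on day 150. A patient enrolled on day e has 120 − e days to the close of recruitment and 150 − e days to the end of analysis. For e between 90 and 120 (month 4) this is 0–30 days and 30–60 days.

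**Assumptions.** The documents give no waiting time and no accrual pattern. I assume uniform accrual over A = 120 days, and F = 0 or 30 days of collection after the last recruit.

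**Fixed wait w.** Share observed = (A + F − w)/A, limited to 0–1. For w = 60 days: (120 − 60)/120 = 50% at F = 0, and (150 − 60)/120 = 75% at F = 30. If all 100 patients were referred, 50 or 25 would have no dermatologist's diagnosis at the cut.

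**Exponential wait with mean m = median/ln 2.**
- Share observed: p = 1 − (m/A)[e^(−F/m) − e^(−(A+F)/m)].
- Mean of observed waits: {m − (m/A)[(F+2m)e^(−F/m) − (A+F+2m)e^(−(A+F)/m)]}/p.

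Example with median 60, F = 30: m = 86.6 and m/A = 0.721. Then p = 1 − 0.721 × (0.707 − 0.177) = 0.617. Observed mean = {86.6 − 0.721 × [203.1 × 0.707 − 323.1 × 0.177]}/0.617 = 39 days.

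| True median (days) | True mean | Observed by day 120 | Observed by day 150 | Observed mean at day 150 |
|---|---|---|---|---|
| 7 | 10 | 92% | 99.6% | 9.9 |
| 14 | 20 | 83% | 96% | 18 |
| 30 | 43 | 66% | 83% | 30 |
| 60 | 87 | 46% | 62% | 39 |
| 90 | 130 | 35% | 48% | 43 |

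At a day-120 cut the observed means for medians of 30, 60 and 90 days are 25, 32 and 34 days. Among month-4 recruits alone, with a median of 60 days, 16% are observed by day 120 and 40% by day 150.

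**Less skewed waits.** For lognormal waits with median 60, mean 68 and log-SD 0.5, simulation gives 46% or 69% observed (day 120 or 150), with observed mean 50 or 55 days.

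**Two checks on a censored analysis (simulation, shares and times assumed).**
- *Remote resolution.* The response labels include follow-up in primary care, so some e-consultations may never lead to a clinic visit. If these are coded as still waiting, a true Kaplan–Meier median of 30 days becomes 54 when 30% are resolved remotely, and is not reached at 50%.
- *Histology.* Suppose biopsy is requested at the clinic visit (median wait 60 days) and the laboratory takes a further median of 14 days. The true median from the primary care visit is 82 days. Kaplan–Meier from that visit, restricted to patients with a biopsy requested by the cut, gives 48 (day 120) or 54 (day 150).

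**The case against.** The strongest case against runs as follows.

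- **No biased estimator is planned.** The Variables section only lists variables, and no section commits to a mean or median of completed waits. Every patient is known from enrolment, so open waits are censored. They become truncated only if dropped. This stands: a reader might infer that the study will report faster access than it delivers, but the documents do not support that as a fact. What they support is that data will be incomplete, that no rule covers the open intervals, and that a summary of completed intervals alone would be biased short.
- **Waits may be short.** The background section describes e-consultation as quick, and with a 14-day median 96% of waits are complete by day 150. This also stands. A reader might infer that late recruits as a group will have no reference diagnosis, but that depends on the undocumented wait. Against it, the same background describes too few dermatologists for the demand, so long waits cannot be ruled out. An e-consultation reply could give an earlier remote opinion, but supplies neither clinic waiting time nor histology.
- **Patient data are not the focus.** The primary questionnaire fits the calendar, the dissemination plan names only the survey results, and the Patient identification section says patient data will not be analysed. This limits the point to secondary variables. It does not remove it while the Variables section and the specialist's procedures still collect them.
- **Non-referred patients** may lack a dermatologist's diagnosis under any calendar. That is a separate gap.

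**Conclusion.** The point holds for the secondary variables that mature after enrolment and for the referral-appropriateness judgement. The calendar and the restriction to study-period data make them incomplete for late recruits. This follows from the design as written and is more than a missing detail. The direction of bias in any completed-interval summary is clear. Its size is not: under uniform accrual and exponential waits it runs from negligible (median 7 days: 9.9 against 10 days at day 150) to severe (median 90 days: 43 against 130, with 48% observed). The primary questionnaire is not affected. The plan should be changed, but the point does not threaten the primary objective.

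**What to change.** 1. Reconcile the Patient identification section with the Variables section and the specialist's procedures, so that it is clear whether patient data are analysed. The remaining steps apply only if they are.
2. State a data-cut date. For each referred patient record one of three states: seen in clinic (date), resolved by e-consultation without a clinic visit (date), or still waiting at the cut.
3. Report waiting time as cumulative incidence, for example the proportion seen within 30 days, with remote resolution as a competing event and open waits censored at the cut.
4. Do not restrict time from the primary care visit to histology to patients with a biopsy already requested by the cut. Either measure from the biopsy request with censoring, or estimate the cumulative incidence of histological diagnosis from the primary care visit in all referred patients, with closure without biopsy as a competing event.
5. Take one records extraction at a stated interval after the last patient's primary care visit, and move the analysis month after it, so that late recruits have a reference diagnosis. For a fixed wait, all are captured once the interval is at least as long as the wait. With exponential waits of median 2 months, 3 months of follow-up captures 81% and 6 months 93%, so steps 3 and 4 are still needed.

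**Cost.** Steps 2 to 4 need a few lines of protocol text and one extra status field. Step 5 delays the final report by the chosen interval. The changes need a written amendment with ethics review (sections 6 and 8). No visits or procedures are added.

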## 2. Theoretical framework. Problem statement.

### Background and rationale

Skin-related diseases are a frequent reason for consultation in primary care (PC); some studies estimate this at approximately 5% of all consultations, mainly among the working population.

This represents a considerable consumption of resources and makes an efficient approach to these conditions a key step in optimizing the functioning of primary care.

Numerous studies show discrepancies in opinion between primary care physicians and dermatologists, with agreement rates in their diagnoses ranging from 57% to 65.52% depending on the study. In general, primary care physicians do not demonstrate adequate knowledge about skin diseases, their diagnosis, and their treatments.

This human limitation when evaluating skin diseases is also reflected in the effort and time required to estimate the degree of involvement in a patient or the stage of the pathology. So much so, that it ends up being a very unrewarding task and can lead to poor adherence to the protocol and inappropriate referrals. Time consumption is especially concerning given that the number of medical professionals, particularly in dermatology, is insufficient to meet the existing demand. Access to a dermatology specialist for the general population is complicated due to the low number (3 dermatologists per 100,000 inhabitants), a situation that is even more difficult in small population centers. Because of this, screening for dermatological lesions must be carried out by primary care physicians, whose diagnostic capacity is even lower and which may increase the risk of misdiagnosis.

In this regard, the literature shows a discrepancy of between 55% and 65% between primary care physicians and specialists, and studies confirm several expected characteristics: common dermatological diseases are often not recognized or are misdiagnosed by non-dermatologists due to the particular profiles of common diagnoses in this field (drug-induced rashes, fungal infections).

In addition to these inherent limitations, when the preliminary examination is performed by the patient, the possibility of bias arises. This is especially true

when the patient knows that the treatment they receive will be determined by the information they provide. Furthermore, the medical team lacks the means to verify the accuracy of the values reported by the patient, preventing external verification.

For several years, and as part of the objectives of utilizing new information and communication technologies (ICTs), healthcare information systems have been adapted to record certain Primary Care (PC) activities. Since June 2020, an asynchronous e-consultation for Dermatology has been available, allowing the transmission of clinical information and images generated in Health Centers to the Dermatology Department of Puerta de Hierro Majadahonda Hospital, integrated within the hospital's own information system (Selene).

The gradual implementation of teledermatology within the strategic plan of the Community of Madrid has culminated in the development of the teleDERMADRID project. Led by [name] and [name] (GAOAIO), in coordination with DGASA, this project enables a new, non-face-to-face consultation modality adapted to the current social and technological reality. This new modality includes an image acquisition management (IAM) tool, accessible via a QR code on the mobile device, which improves and streamlines the e-consultation. This tool is directly linked to the integrated request system (SIPE), ensuring rapid and generally satisfactory access to and response to the health problems of the target population, thus avoiding diagnostic delays, unnecessary travel, and expediting the therapeutic requirements available in our service portfolio.

The reduction of pressure on in-person hospital consultations directly contributes to lower costs for conventional care. All of this is achieved without compromising the humanization of patient care, another key objective for improving health-related quality of life. In addition to the image management tool, a clinical form is associated with the necessary items to complement the image.

Advancing the development of ICTs, the emergence of Artificial Intelligence in medicine has enabled the automation of a wide variety of processes, such as patient triage, allowing for faster care for those suffering from more serious conditions. The use of these types of systems by primary care physicians can increase their diagnostic capacity by up to 12%, proving highly useful in appropriate referrals for patients with skin conditions.

Therefore, this study aims to clinically validate a novel artificial intelligence tool to increase the appropriateness of referrals from primary care to dermatology.

---

## Research Questions

The questions this study seeks to answer are the following:

- Does dermatological artificial intelligence help primary care physicians treat patients with skin problems?
- Does Legit.Health's cutaneous artificial intelligence contribute to appropriate referrals?
- Do primary care physicians value the incorporation of dermatological artificial intelligence into their routine clinical practice?

## Hypothesis

The hypothesis guiding this study is that the Legit.Health platform, developed by AI LABS GROUP SL, significantly increases the appropriateness of referrals to dermatology.

This hypothesis is based on the notion that artificial intelligence introduces several significant changes to the diagnostic process:

- Greater sensitivity and specificity than a primary care physician in diagnosing skin conditions, especially in differentiating between malignant and benign lesions.
- It provides the security of a clinically validated second medical opinion.

## 3. Primary and secondary objectives

The main objective of this study is to validate the clinical utility of the Legit.Health platform, developed by AI LABS GROUP SL, in the management of patients with skin conditions by primary care physicians and dermatologists at the Puerta de Hierro Majadahonda University Hospital involved in the project.

Secondary objectives include:

- Reduce and correct the referral of patients with skin conditions from primary care to dermatology.
- Personalize and improve continuing education for primary care physicians in the field of dermatology.
- Offer healthcare adapted to technological innovations.
- Measure the satisfaction of primary care physicians with the Legit.Health platform.
- Measure the satisfaction of dermatologists with the Legit.Health platform.

---

## 4. Methods

### Study design

This is a prospective, observational, analytical study of a series of clinical cases.

It is a longitudinal study.

### Study population. Inclusion & exclusion criteria

Adult patients ( $\geq 18$  years) with skin pathologies.

#### Inclusion criteria:

- Patients with suspected of having the following pathologies in Primary Care:
  - Tumor pathology
    - Benign
      - Histiocytoma
      - Seborrheic keratosis
      - Angiomas
    - Precancerous
      - Actinic Keratosis
    - Suspected malignancy:
      - Basal cell carcinoma
      - Squamous cell carcinoma
    - Pigmented lesions
      - Melanocytic nevus
      - Malignant melanoma
  - Inflammatory pathology
    - Psoriasis
    - Atopic dermatitis
    - Urticaria

- Hidradenitis suppurativa
- Lichen planus
- Infectious pathology
  - Viral warts
  - Molluscs
  - Herpes simplex
- Patients aged 18 years or older.
- Patients who have signed the informed consent for the study.

**Exclusion criteria:**

- Patients under 18 years of age.
- Pregnant patients.
- Patients who, in the researcher's opinion, will not comply with the study procedures.

**Variables**

The main variable aims to determine the clinical utility of the platform developed by AI LABS GROUP SL in the management of patients with skin pathology by primary care physicians and dermatologists of the Puerta de Hierro Majadahonda University Hospital involved in the project.

For this purpose, clinicians will complete the **Clinical Utility and Satisfaction Questionnaire (Annex I)**.

In addition, the following secondary variables will be collected::

- Patient demographics:
  - Sex
  - Age
- Teleconsultation data:
  - Response time
  - Response label (follow-up in primary care, shared follow-up, dermatology follow-up, insufficient or inadequate information)
- Data from the in-person consultation:

- Duration of an in-person dermatology appointment to respond to an online primary care consultation.
- Waiting time until being seen in a specialized dermatology clinic.
- Diagnosis
  - Diagnostic correlation between primary care and dermatology.
  - Number of patients referred by pathology.
  - Diagnostic correlation between primary care, dermatology, and dermatopathology (if applicable).
  - Time elapsed between the day of the primary care visit and the day of the histopathological diagnosis (if applicable).
- Primary care physician satisfaction using the Clinical Utility and Satisfaction Questionnaire (Appendix I).
- Dermatologists satisfaction using the Clinical Utility and Satisfaction Questionnaire (Appendix I).

### **Expected sample size**

This study will recruit 100 patients. This study is designed as a proof-of-concept pilot study in which the sample size has been estimated based on the number of primary care physicians who treat patients diagnosed with skin diseases who can be seen in the primary care services of the following centers:

1. Majadahonda Health Center
2. Pozuelo Health Center

During the study recruitment period, all patients diagnosed with skin diseases who meet the selection criteria will be included.

To ensure that all primary care physicians participating in the study have sufficiently interacted with the tool, a minimum of 50 patients per primary care center is required.

The data collected from these patients during the study period will be analyzed, and based on the results, an assessment will be made as to whether it is necessary to expand the sample size to include more patients.

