## 11. Annexes

### Annex I - Clinical Utility and Satisfaction Questionnaire

Based on their experience, without needing to consult the Medical History:

1. Average weekly number of patients with skin conditions you have seen in your practice during the last two months (approximate).
2. Name the conditions for which Legit.Health has been most useful in your daily clinical practice.
3. In your opinion, indicate the impact of Legit.Health from 0 to 10 (where 0 is “no impact” and 10 is “great impact”) on the accuracy of your diagnostic decisions for each of the following diseases:
  - a. Urticaria
  - b. Psoriasis
  - c. Hidradenitis Suppurativa
  - d. Melanoma
  - e. Atopic Dermatitis
  - f. Other (add any other diseases where the tool has had an impact at this point and rate the impact from 0 to 10)
4. In your opinion, please indicate the impact of Legit.Health from 0 to 10 (where 0 is “no impact” and 10 is “great impact”) in relation to reducing the time to issue your diagnostic decision for each of the following diseases:
  - a. Urticaria
  - b. Psoriasis
  - c. Hidradenitis Suppurativa
  - d. Melanoma
  - e. Atopic Dermatitis
  - f. Other (add any other conditions where the tool has had an impact at this point)
5. In your opinion, please indicate the impact of Legit.Health from 0 to 10 (where 0 is “no impact” and 10 is “great impact”) on your therapeutic decision-making, thanks to the included management recommendations, for each of the following diseases:
  - a. Urticaria
  - b. Psoriasis
  - c. Hidradenitis Suppurativa

- 
- d. Melanoma
  - e. Atopic Dermatitis
  - f. Other (add any other conditions where the tool has had an impact at this point)
6. In your opinion, please indicate the impact of Legit.Health from 0 to 10 (where 0 is “no impact” and 10 is “great impact”) on monitoring the evolution of skin lesions for each of the following diseases:
- a. Urticaria
  - b. Psoriasis
  - c. Hidradenitis Suppurativa
  - d. Melanoma
  - e. Atopic Dermatitis
  - f. Other (add any other conditions where the tool has had an impact at this point)
7. In your opinion, please indicate the impact of Legit.Health from 0 to 10 (where 0 is “no impact” and 10 is “high impact”) on the efficiency of interconsultations/referrals to the dermatology service (in cases where referral applies) for each of the following diseases:
- a. Urticaria
  - b. Psoriasis
  - c. Hidradenitis Suppurativa
  - d. Melanoma
  - e. Atopic Dermatitis

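### Eligibility wording shifts between suspected and diagnosed and prior specialist diagnosis is not recorded, so known cases can raise primary care–dermatology agreement by an unknown amount

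*Combined protocol and SAP*

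**What the plan says.** The protocol describes the population in two ways.

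- **Suspected.** The first inclusion criterion (section 4) reads "Patients with suspected of having the following pathologies in Primary Care". The disease row of the Abstract agrees: "Patients suspected of having the following pathologies in Primary Care: tumor pathology, inflammatory pathology, and infectious pathology".
- **Diagnosed, or having the condition.** Expected sample size (section 4) describes patients who already carry a diagnosis, once as the basis for the number and once as the enrolment rule: "During the study recruitment period, all patients diagnosed with skin diseases who meet the selection criteria will be included". The population row of the Abstract speaks of patients attending with the pathology.

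There are three exclusion criteria: age under 18, pregnancy, and "Patients who, in the researcher's opinion, will not comply with the study procedures". None concerns an existing diagnosis. The list under Variables has no item for prior diagnosis.

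The outcome affected is a secondary variable, "Diagnostic correlation between primary care and dermatology". Its data come from the specialist procedures in section 5: "The initial diagnosis provided by the primary care physician, as well as their own diagnosis, will be documented". The main variable is the physician questionnaire in Annex I.

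**The concern.** Agreement between a primary care physician and a dermatologist is informative about diagnostic performance only if the first diagnosis was reached without knowledge of the second. If dermatology or histology has already settled the condition, the primary care physician may know the answer. The specialist's diagnosis is then no longer an independent reference. Agreement in such a patient says little about the physician or the tool.

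The conditions listed under Inclusion criteria make this foreseeable. Psoriasis, atopic dermatitis, hidradenitis suppurativa and lichen planus can all be long-standing. Known cases may also involve no new referral decision, so the referral variables would mix open decisions with settled ones. Without a field for prior diagnosis, the two groups could not be reliably separated at analysis.

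**Working it through.** **1. The plan's own figure.** Two centres with a minimum of 50 patients each give 2 × 50 = 100, which matches the stated total. No target agreement, precision or power is given, so there is no planned agreement figure to reproduce.

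**2. Does the text close the gap?** The enrolment sentence sends the reader back to the selection criteria. Those say suspected but do not define it as new or not yet diagnosed by a specialist. Neither the exclusions nor the variables address the point. Known cases are therefore neither clearly admitted nor clearly kept out, and they are not identified.

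**3. Direction and size of the bias.** Inputs:

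- p, agreement in new cases. Background and rationale describes physicians and dermatologists "with agreement rates in their diagnoses ranging from 57% to 65.52% depending on the study", so p = 0.57 to 0.6552. The same section later gives a discrepancy of 55% to 65%, which implies p = 0.35 to 0.45. The two statements conflict.
- a, agreement in known cases. Assumed 1.00, with 0.95 as a sensitivity value.
- f, the share of known cases among patients with both diagnoses recorded. Not in the documents, so assumed over a range.

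Observed agreement = f·a + (1 − f)·p, so the bias is f·(a − p).

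For f = 0.10:

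| p | a = 1.00 | a = 0.95 |
|---|---|---|
| 0.57 | 0.10 × 0.43 = 4.3 points | 0.10 × 0.38 = 3.8 points |
| 0.6552 | 0.10 × 0.3448 = 3.4 points | 0.10 × 0.2948 = 2.9 points |
| 0.35 | 0.10 × 0.65 = 6.5 points | 0.10 × 0.60 = 6.0 points |
| 0.45 | 0.10 × 0.55 = 5.5 points | 0.10 × 0.50 = 5.0 points |

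Observed agreement with a = 1.00 and p = 0.57 to 0.6552:

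- f = 10%: 61.3% to 69.0%
- f = 20%: 65.6% to 72.4%
- f = 30%: 69.9% to 75.9%

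**4. Which denominator?** Under section 5, the primary care physician refers only when this is judged necessary, and the dermatologist records both diagnoses for the patients seen. So f is not the share F among all enrolled. If known and new cases are referred at rates r1 and r0, then f = F·r1 / (F·r1 + (1 − F)·r0). Take F = 20% (assumed):

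- Known cases referred half as often: f = 0.10 / (0.10 + 0.80) = 11.1%. The bias is 0.111 × 0.3448 to 0.111 × 0.43, or 3.8 to 4.8 points.
- Equal referral: f = 20%, and the bias is 6.9 to 8.6 points.
- Known cases referred twice as often: f = 0.40 / (0.40 + 0.80) = 33.3%, and the bias is 11.5 to 14.3 points.

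**5. Scale.** If all 100 patients had both diagnoses, the 95% half-width would be 1.96 × √(p(1 − p)/100), or 9.3 to 9.7 points. With 50 such patients it would be 13.2 to 13.7 points.

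**The case against.** The strongest reply is that the enrolment sentence is subordinate to the criteria, and in ordinary usage a patient with confirmed psoriasis is not suspected of psoriasis. On that reading, known cases are already out and only the wording of the sample size section is loose. This stands in part: the documents nowhere say that known cases will be enrolled. But the ordinary reading is not written down, and a site following the sample size section could reasonably admit them.

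Second, the procedures have the physician diagnose from direct examination with the tool's output as a guide, and say nothing of copying from the record. That is also fair, so non-independence is a risk and not a described practice. Nothing keeps the physician unaware of an earlier diagnosis, however.

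Third, agreement is secondary in a proof-of-concept pilot, and Patient identification (section 5) says patient data will not be analysed. The first part stands and limits the weight of the point. The second does not dispose of it, because Variables lists patient-level items and Expected sample size says the patients' data will be analysed.

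A reader might infer more than the documents support:

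- *That agreement would be driven close to 100%.* With a = 1.00, reaching 90% needs f = (0.90 − 0.6552)/0.3448 = 71% to (0.90 − 0.57)/0.43 = 77%. Known cases would have to be most of the assessed patients.
- *That known cases would mimic the gain of up to 12% credited to such tools in section 2.* That figure concerns diagnostic capacity and is not stated to be absolute points of agreement. No comparison with it, or with the literature agreement rates, is planned.
- *That Annex I item 6, "on monitoring the evolution of skin lesions for each of the following diseases", shows known cases are intended.* Newly presenting lesions can also be followed over time.
- *That the main variable is inflated.* Known cases leave the tool little to add to diagnostic accuracy (Annex I item 3), so any effect on those ratings is probably downward. It cannot be computed from the documents.

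**Conclusion.** The point holds as a gap in definition and recording. The eligibility wording is inconsistent, prior specialist diagnosis is neither excluded nor captured, and any such patients who reach the agreement variable bias it upward without any contribution from the tool.

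The size of the bias is unknown. The illustrative 3.4 to 4.3 points per 10% of known cases rests on three things: the first of two conflicting background rates as the agreement in new cases, full agreement in known cases, and a share counted among patients with both diagnoses recorded. At 95% agreement in known cases it is 2.9 to 3.8 points. On the conflicting background figures, with full agreement, it is 5.5 to 6.5 points. If the tool itself raises agreement in new cases, the bias per known case is smaller.

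This is a cheap improvement affecting secondary variables. It does not undermine the main questionnaire outcome.

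**What to change.** 1. Use *suspected of having* consistently in the Abstract (population row), Inclusion criteria and Expected sample size (both places).
2. Add one yes/no field at entry: index condition previously diagnosed by dermatology or histology.
3. Report diagnostic correlation and the referral variables primarily in patients marked *no*, with all patients as a secondary report. State the number with both diagnoses recorded in each group.
4. Reconcile the two background agreement statements before using either as a benchmark.

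A new exclusion is not needed. The study objective covers management, and Annex I items 5 and 6 ask about treatment decisions and monitoring, where known cases may be informative.

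The cost is a few words and one field in the data collection document. The downside is fewer patients behind the main agreement and referral estimates, hence wider intervals. For example, if 20% of 100 assessed patients were marked *yes*, 80 would remain, and the half-width would grow by a factor of √(100/80) = 1.12.
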